AST aspartate aminotransferase
β-hCG human chorionic gonadotropin

BARS Barnes Akathisia Scale
BMI body mass index
BP blood pressure

C-SSRS Columbia-Suicide Severity Rating Scale

CFR Code of Federal Regulations
CRO Contract research organization

CSR Clinical study report

DSM-5 Diagnostic and Statistical Manual, 5th edition ECG electrocardiogram, electrocardiographic

eCRF electronic case report form
ECT electroconvulsive therapy
EDC electronic data capture
ET early termination

FDA Food and Drug Administration FOCBP Female of childbearing potential

FR Federal Register
GCP Good Clinical Practice

HIPAA Health Insurance Portability and Accountability Act of 1996

ICF informed consent form

ICH International Council on Harmonisation of Technical

Requirements for Registration of Pharmaceuticals for

Human Use

IEC International Ethics Committee

IND Investigational New Drug (application)

IRB Institutional Review Board
ITI Intra-Cellular Therapies, Inc.
IWRS Interactive Web Response System

MADRS Montgomery-Åsberg Depression Rating Scale

MDD major depressive disorder MDE major depressive episode

PK pharmacokinetic

QTc QT interval corrected for heart rate

QTcB QT interval corrected for heart rate using the Bazett formula

 $(QTcB = QT/\langle RR \rangle^{1/2})$

OTcF QT interval corrected for heart rate using the Fridericia

formula (QTcF = QT/ $\langle RR \rangle^{1/3}$)

SAE serious adverse event SAP Statistical Analysis Plan SAS Simpson Angus Scale

SOC system organ class

TEAE treatment-emergent adverse event

UDS urine drug screen ULN upper limit of normal

1. PROTOCOL SYNOPSIS AND SCHEDULE OF EVALUATIONS

CLINICAL STUDY SYNOPSIS:	Study ITI-007-503
Title of Study	An Open-label, Multicenter Trial to Assess the Safety and Tolerability of Lumateperone as Adjunctive Therapy in the Treatment of Patients with Major Depressive Disorder
Study Centers (Country)	Approximately 120 study centers (US and Non-US)
Development Phase	Phase 3
Objectives	Primary Objective To evaluate the safety and tolerability of lumateperone 42 mg administered orally once daily for approximately 26 weeks as adjunctive treatment to antidepressant therapy (ADT) in patients with major depressive disorder (MDD). Secondary Objectives To evaluate whether lumateperone 42 mg administered orally once daily for approximately 26 weeks as adjunctive treatment to ADT improves or maintains improvement of depressive symptoms in patients with MDD as measured by change from baseline in the Montgomery-Åsberg Depression Rating Scale (MADRS) total score and in the Clinical Global Impression Scale-Severity (CGI-S) score.
Study Design	This is an international, multicenter, open-label, fixed dose, 26-week study of patients with MDD. Eligible patients from the lead-in studies will enter the Open-label Safety Study at the Screening/Baseline Visit (Visit 1/Day 1), at which point patient eligibility will be assessed and informed consent obtained. At the Screening/Baseline Visit (Visit 1/Day 1), which is the same visit as Visit 8/Day 43 of the lead-in study, eligible patients will receive open-label lumateperone 42 mg once daily for approximately 26 weeks. Patients will continue their background ADT from the lead-in study. Patients will be seen for weekly visits through Visit 5/Week 4. Thereafter, visits will occur every two weeks. A Safety Follow-up visit will occur on Visit 17/Day 197, approximately 2 weeks after the last dose of open-label lumateperone 42 mg.
Number of Patients	Approximately 760 patients are planned to be enrolled in the Open-label Safety Study. No de novo patients will be enrolled.

Diagnosis and Main Criteria for Main Inclusion Criteria Inclusion and Exclusion Each patient entering the Open-label Safety Study must meet all of the following criteria: 1. In the opinion of the Investigator, the patient must have safely completed the lead-in study. 2. The patient must understand the written informed consent for the Open-label Safety Study, provide signed and witnessed written informed consent. 3. The patient is taking his/her ADT as prescribed from the lead-in study. The patient must agree to continue using highly effective methods of birth control as specified in the lead-in study through the Safety-Follow-up Period of the Open-label Safety Study, or female patients or female partners of male patients must be of non-childbearing potential. All Inclusion Criteria are presented in Section 6.3.1. Main Exclusion Criteria Because all patients enrolled in the lead-in study were required to satisfy exclusion criteria for participation in the lead-in study, the Investigator should assess if there has been any change in patient health status. Any newly-emergent medical condition reported during the lead-in study must be evaluated by the Investigator and should be discussed with the Sponsor or designee before enrolling the patient in the study. Patients enrolling directly from the lead-in study to the Open-label Safety Study at Visit 1/Day 1 will be excluded if they meet the following criteria: 1. In the opinion of the Investigator, the patient is unable to comply with study procedures or judged to be inappropriate for the study; In the opinion of the Investigator, the patient has a significant risk for suicidal behavior during the course of her/his participation in the study or is considered to be an imminent danger to her/himself or others, and/or: At the Screening/Baseline Visit (Visit 1/Day 1) the patient scores "yes" on Suicidal Ideation Items 4 and 5 of the C-SSRS since the last visit version (Visit 7/Week 5 of the lead-in studies); At the Screening/Baseline Visit (Visit 1/Day 1), the patient scores \geq 5 on MADRS Item 10 (Suicidal Thoughts); Based on the Investigator's clinical judgement, any abnormal clinical laboratory tests results obtained throughout the lead-in study that are considered clinically significant and preclude safe participation in All Exclusion Criteria are presented in Section 6.3.2. **Duration of Study** Study duration will be approximately 26 weeks of open-label treatment, followed by a 2-week Safety Follow-up. **Investigational Product, Dosage, and Lumateperone** 42 mg capsules, 42 mg/day adjunctive to ongoing

Confidential Page 11

background ADT, oral administration.

Mode of Administration

Criteria for Evaluation	
Safety Measures	AE recording, clinical laboratory measures, vital signs, electrocardiograms (ECGs), and physical examination; measures of extrapyramidal symptoms: Abnormal Involuntary Movement Scale (AIMS), Barnes Akathisia Rating Scale (BARS), and Simpson Angus Scale (SAS); Columbia-Suicide Severity Rating Scale (C-SSRS); and pregnancy test (if applicable).
Efficacy Endpoints	Change from baseline in MADRS total score and CGI-S score.
Pharmacokinetic Measures	Optional blood samples for pharmacokinetic (PK) analysis of lumateperone and metabolites (IC200131, IC200161, IC200565, IC201308, and IC201309) will be collected. Three blood samples will be collected at Visit 2 at predose, between 0.5-to-1-hour postdose, and between 1.5 to 3 hours postdose. One sample will be collected at Visit 7.
Statistical Methods and Sample Size	Approximately 760 patients will be enrolled. The sample size is not based on statistical considerations, but is based on the number of patients who may be eligible based on participation in the lead-in study. It is expected that the majority of patients who safely complete the lead-in study will continue treatment for the full 26 weeks.
	All safety parameters will be summarized descriptively. Safety analyses will be based on the Safety Population defined as all patients who received at least one dose of open-label lumateperone 42 mg.
	Analyses of efficacy endpoints will be performed based on the patients in the Safety Population who have an available baseline efficacy value and at least one postbaseline efficacy assessment during the Open-label Treatment Period. Analyses will primarily consist of change from baseline descriptive summaries of MADRS total score and CGI-S scores.
	Individual plasma concentrations of lumateperone and metabolites will be listed and summarized by visit/timepoint. Plasma concentrations of lumateperone and potentially of selected metabolites will be analyzed using a population PK approach. The results from the population PK analyses will be presented in a separate report.

Table 1-1: Schedule of Evaluations

Study Period	Screening /Baseline Visit ¹		Open-label Treatment Period ² Fo													Safety Follow Up	
Visit Number	1	2	3	4	5	6	7	8	9	10	11	12	13	14	15	16/ET	17
Study Day	1	8	15	22	29	43	57	71	85	99	113	127	141	155	169	183	197
Study Week	0	1 (+/-3 days)	2 (+/-3 days)	3 (+/-3 days)	4 (+/-3 days)	6 (+/3 days)	8 (+/-3 days)	10 (+/-3 days)	12 (+/-3 days)	14 (+/-3 days)	16 (+/-3 days)	18 (+/-3 days)	20 (+/-3 days)	22 (+/-3 days)	24 (+/-3 days)	26 (+/-3 days)	28 (+/-3 days)
Informed consent	X																
Inclusion/Exclusion criteria	X																
Physical examination	X															X	
Vital signs³	X	X	X	X	X	X	X	X	X	X	X	X	X	X	X	X	X
12-lead ECG ⁴	X	X					X				X					X	
Clinical laboratory assessments (hematology, serum chemistry, urinalysis) ⁵	X	X					X				X					X	
Urine drug testing ⁶	X	X					X				X					X	
Serum/urine pregnancy test ⁷	X	X			X		X		X		X		X		X	X	
MADRS	X	X	X	X	X		X		X		X		X		X	X	X
CGI-S	X	X	X	X	X		X		X		X		X		X	X	
AIMS/BARS/SAS	X	X			X		X		X		X		X		X	X	
C-SSRS	X	X	X	X	X	X	X	X	X	X	X	X	X	X	X	X	X
PK sampling		X8					X9										
AEs/SAEs	X	X	X	X	X	X	X	X	X	X	X	X	X	X	X	X	X
Concomitant medications	X	X	X	X	X	X	X	X	X	X	X	X	X	X	X	X	X
ADT prescription dispensation ¹⁰	X																
ADT compliance check	X	X	X	X	X	X	X	X	X	X	X	X	X	X	X	X	

Study Period	Screening /Baseline Visit ¹		Open-label Treatment Period ² Fo											Safety Follow Up			
Visit Number	1	2	3	4	5	6	7	8	9	10	11	12	13	14	15	16/ET	17
Study Day	1	8	15	22	29	43	57	71	85	99	113	127	141	155	169	183	197
Study Week	0	1 (+/-3 days)	2 (+/-3 days)	3 (+/-3 days)	4 (+/-3 days)	6 (+/3 days)	8 (+/-3 days)	10 (+/-3 days)	12 (+/-3 days)	14 (+/-3 days)	16 (+/-3 days)	18 (+/-3 days)	20 (+/-3 days)	22 (+/-3 days)	24 (+/-3 days)	26 (+/-3 days)	28 (+/-3 days)
Lumateperone dispensation	X	X	X	X	X	X	X	X	X	X	X	X	X	X	X		
Lumateperone return and compliance check		X	X	X	X	X	X	X	X	X	X	X	X	X	X	X	

AE = adverse event; AIMS = Abnormal Involuntary Movement Scale; BARS = Barnes Akathisia Scale; CGI-S = Clinical Global Impression Scale-Severity; C-SSRS = Columbia Suicide Severity Rating Scale; ECG = electrocardiogram; ET = Early Termination; HbA1c = hemoglobin A1c; MADRS = Montgomery-Åsberg Depression Rating Scale; MINI = Mini-International Neuropsychiatric Interview; PK = pharmacokinetic; SAE=Serious Adverse Event; SAS=Simpson Angus Scale.

- The Screening/Baseline Visit (Visit 1/Day 1) is the same visit as Visit 8/Day 43 of the lead-in study. In addition to the specified Inclusion and Exclusion criteria for this Open-label Safety Study, medical, psychiatric, and medication histories from the lead-in study will be considered for eligibility at the Screening/Baseline Visit of the Open-label Safety Study. A MINI would not be repeated at the Screening/Baseline Visit (Visit 1/Day 1).
- During the Open-label Treatment Period, if the patient is unable to travel to the site for an in-person visit or if sites are unable to schedule in-person visits (eg, a natural disaster, pandemic), sites will be permitted to conduct remote visits with approval from the Sponsor or designee. If on-site laboratory and ECG assessments are not feasible, local laboratory and ECG testing are permitted if determined clinically necessary by the Investigator. Remote assessments of MADRS, CGI-S, C-SSRS, and AIMS, BARS, SAS may also be performed, if feasible. Screening/Baseline Visit (Visit 1/Day 1) must be performed in person.
- Height and BMI will only be collected at Visit 1 and waist circumference will only collected at Screening/Baseline Visit (Visit 1/Day 1) (which is the same as Visit 8/Day 43 of the lead-in study) and Visit 16/ET.
- ECGs will be collected at Screening/Baseline Visit (Visit 1/Day 1; which is the same as Visit 8/Day 43 of the lead-in study), Visit 2, Visit 7, Visit 11, and Visit 16/ET. Unscheduled visits for repeat ECG assessments may be performed at any time for safety reasons or at the discretion of the Investigator.
- Clinical laboratory assessments are to be taken after an overnight fast of at least 10 hours and will be collected at Screening/Baseline Visit (Visit 1/Day 1; (which is the same as Visit 8/Day 43 of the lead-in study), Visit 2, Visit 7, Visit 11, and Visit 16/ET. HbA1c and TSH (reflex free T3 and T4) collected at Screening/Baseline Visit (Visit 1/Day 1) and Visit 16/ET. Unscheduled visits for repeat laboratory assessments may be performed at any time for safety reasons or at the discretion of the Investigator. Hepatitis serology, performed in the lead-in study, will not be repeated at the Screening/Baseline Visit of the Open-label Study.
- An unscheduled urine drug test may be conducted at any time during the study at the Investigator's discretion.
- Female patients of childbearing potential must have a negative urine pregnancy test. Because the Screening/Baseline Visit (Visit 1/Day 1) serum pregnancy test results will not be available at the Screening/Baseline Visit (Visit 1/Day 1), patients will be discontinued immediately upon receipt of a positive serum pregnancy test result. For all other visits, a urine pregnancy test will be performed. Unscheduled pregnancy tests may be administered at any time during the study at the Investigator's discretion.

Protocol ITI-007-503 23 Aug 2021

Patients who consent to PK sampling will take the evening dose the day before Visit 2; the date and time of this dose should be recorded as reported by the patient. At Visit 2, patients will be administered the Visit 2 dose of lumateperone at the study site after an overnight fast of at least 10 hours and will continue to fast for at least 2 hours after dosing. The date and time of lumateperone administration at Visit 2 must be recorded. PK sampling will be collected at Visit 2 at predose (within 30 minutes prior to dosing), between 0.5 hour and 1-hour post-dose and between 1.5 hour and 3 hours post-dose. The date and time of PK sample collection at each timepoint must be recorded. Patients will be instructed not to take an evening dose of lumateperone at Visit 2. The next dose of lumateperone should be taken the next evening as prescribed. ADT should be taken as prescribed throughout the PK sampling period.

- Patients who consent to PK sampling will have one blood sample collected at Visit 7. The patient-reported date and time of lumateperone administration prior to PK sampling on the evening before Visit 7 should be recorded. The date and time of PK sample collection must be recorded.
- Antidepressant prescriptions will be provided to patients as needed through the duration of the study.

2. ETHICAL CONSIDERATIONS

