8.2.7.2.3 Simpson-Angus Scale

The SAS is a measure of extrapyramidal side effects (Simpson & Angus, 1970). The SAS is used for assessment of antipsychotic-induced parkinsonism in both clinical practice and research settings. Ten items including rating gait, arm dropping, shoulder shaking, elbow rigidity, wrist rigidity, leg pendulousness, head dropping, glabella tap, tremor, and salivation are rated on a scale from 0 (normal) to 4 (extreme in severity). The SAS should be conducted by the investigator or an expert site-based rater in a room where the patient can walk a sufficient distance to allow a natural pace (eg, 15 paces). Each side of the body should be examined. The SAS is to be completed at Screening/Baseline (Visit 1/Day 1) and Visits 2, 5, 7, 9, 11, 13, 15, and 16/ET as specified in the Schedule of Evaluations (Table 1-1).

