10.5.3 Simpson-Angus Rating Scale (SAS)

Descriptive statistics for SAS total score at baseline and changes from baseline at each assessment visit (including the end of the Open-label Treatment Period) will be presented for the Safety Population.

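### The schedule footnote allows the Simpson-Angus Scale to be rated remotely, which conflicts with the protocol's own description of the examination, and the SAP pools any such ratings with in-person ones

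*Protocol*

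**What the plan says.** Footnote 2 of protocol Table 1-1 covers visits in the Open-label Treatment Period that cannot be held in person. In that case "sites will be permitted to conduct remote visits with approval from the Sponsor or designee". For laboratory tests and ECG the footnote offers local testing. For the rating scales it says "Remote assessments of MADRS, CGI-S, C-SSRS, and AIMS, BARS, SAS may also be performed, if feasible". The only visit it fixes as in person is the first: "Screening/Baseline Visit (Visit 1/Day 1) must be performed in person". SAP Table 2-1 carries the same footnote.

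Protocol 8.2.7.2.3 describes the SAS as done by the investigator or a site-based rater, in a room with enough space for the patient to walk. It adds: "Each side of the body should be examined". After gait, the items are "arm dropping, shoulder shaking, elbow rigidity, wrist rigidity, leg pendulousness, head dropping, glabella tap, tremor, and salivation", each scored 0 to 4. The scale is scheduled at Visit 1 and at Visits 2, 5, 7, 9, 11, 13, 15 and 16/ET.

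SAP 10.5.3 plans "Descriptive statistics for SAS total score at baseline and changes from baseline at each assessment visit", with no split by how the rating was made. For repeated or unscheduled SAS ratings, SAP 15.2 takes the last non-missing value in the window. Neither document says which SAS items may be rated remotely, how an item that could not be examined is scored, whether a partial total counts, or whether visit mode is recorded.

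**The concern.** A rater on a video link cannot carry out 8.2.7.2.3 as written. The footnote nevertheless groups the SAS with interview-based scales such as the MADRS and C-SSRS, and offers no in-person alternative of the kind it gives for ECG and laboratory tests. Since only Visit 1 has to be in person, any of the eight later SAS ratings could be remote.

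Safety and tolerability is the primary objective. Of the three movement scales, AIMS covers involuntary movements and BARS covers akathisia, so the SAS is the one directed at parkinsonism. The scheduled physical examination, which includes a neurological part, takes place only at Visit 1 and Visit 16/ET. Between those visits the SAS is the only scheduled examination for rigidity. If incomplete remote examinations enter the visit summaries unmarked, a reader of the report cannot tell a low score from an item that was never examined.

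**Working it through.** The documents give no figure for this point, so there is none to reproduce. The check uses the scale as 8.2.7.2.3 describes it, plus two stated assumptions.

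**Inputs**
- Items and scoring: 10 items, each 0 to 4 (protocol 8.2.7.2.3). Maximum total = 10 × 4 = 40.
- k, the number of items that cannot be examined remotely: not in the documents. From the names, a narrow count takes shoulder shaking, elbow rigidity, wrist rigidity and glabella tap (k = 4). Adding leg pendulousness and head dropping gives 6, and arm dropping makes 7. Assumed range: 4 to 7.
- f, the share of SAS ratings at a visit that are remote: not in the documents. Assumed range: 5% to 50%.
- Planned enrolment: about 760 (protocol synopsis).

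**Case A: items not examined are scored 0 or left out of the sum**

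Highest possible remote total = 4 × (10 − k).

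| k | Highest remote total | Points that cannot register |
|---|---|---|
| 4 | 24 | 16 |
| 5 | 20 | 20 |
| 6 | 16 | 24 |
| 7 | 12 | 28 |

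This is a limit on the possible range. For the visit mean, let every item have the same expected score m. In-person totals then average 10m and remote totals (10 − k)m, so the visit mean is (1 − f) × 10m + f × (10 − k)m = 10m − fkm. The relative fall is f × k/10:
- f = 5%, k = 4: 0.05 × 0.4 = 2.0%
- f = 10%, k = 6: 0.10 × 0.6 = 6.0%
- f = 50%, k = 7: 0.50 × 0.7 = 35%

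The mean change from baseline falls by the same absolute amount, fkm points. The documents give no expected SAS score, so m is unknown and this cannot be put in points.

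**Case B: totals are prorated from the rated items**

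With equal item scores the bias is 0. With unequal scores it can go either way. Take k = 5 and a true total of 10. If the signs are five items at score 2, all among the observable items, the prorated total is 10 × 10/5 = 20. If the same signs are all in the hands-on items, it is 0.

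**Case C: the total is set to missing**

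No total is lowered, but data are lost: 760 × 0.05 = 38 to 760 × 0.50 = 380 patients at a visit, if all planned patients were still attending.

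**Window rule**

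Suppose a patient has an in-person SAS and later, in the same window, a remote repeat. SAP 15.2 selects the later non-missing value, so the incomplete examination replaces the complete one.

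The direction and size therefore depend on a scoring practice and a remote share that the plan does not give.

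**The case against.** Four points can fairly be made against this.

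- **Remote visits are an exception.** They need an obstacle such as a disaster or pandemic and Sponsor or designee approval, and the scales are further limited by feasibility. That qualifier can be read as ruling out an SAS that cannot be done. This lowers the likely number of remote ratings. It does not settle the conflict: approval attaches to the visit and not to the scale, feasibility is undefined, and the SAS is named among the scales that may be done.
- **Parkinsonism is captured elsewhere.** SAP 10.1 and Table 10-1 tabulate extrapyramidal adverse events, including parkinsonism, cogwheel rigidity and tremor, and adverse events are queried at every visit. This stands and limits the consequence. Those events are elicited by a non-leading question, however, which does not replace examining for rigidity.
- **The summaries are descriptive**, in a single-arm study with no test on the SAS. That also stands.
- **Dropping remote totals discards observable items**, such as gait, tremor and salivation. Listing the remote item ratings keeps that information.

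A reader might also infer that every remote rating is compared with an in-person baseline. The documents do not support that. The in-person rule covers Visit 1/Day 1 of this study, whereas protocol 9.1 and SAP section 10 define baseline as the last value before the first double-blind dose in the lead-in study. How that value was rated is not stated.

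**Conclusion.** The conflict between footnote 2 and protocol 8.2.7.2.3 is real, and the SAP lets remote ratings into the SAS summaries unmarked. This is a cheap improvement to a safety summary. It is not evidence that the trial's safety conclusions are wrong.

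Remote totals can understate parkinsonism if items that cannot be examined are scored 0 or omitted, with a ceiling of 24 to 12 out of 40 for 4 to 7 such items. Under that scoring and equal item scores, the visit mean would fall by between 2.0% and 35% over the assumed ranges of k and f.

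Three stronger readings are tempting but not supported:
- That remote totals will be too low. This follows only under one scoring practice; proration can err either way, and a missing total lowers nothing.
- That most of the scale needs hands-on contact. The protocol describes no manoeuvres, the count rests on item names, and 4 or 5 of ten is not most.
- That a loss of 60 to 70% of the range (24 or 28 of 40 points, for 6 or 7 items) measures the bias. It is a loss of possible range and not a bias in any reported mean.

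**What to change.** 1. In footnote 2 of protocol Table 1-1 and SAP Table 2-1, remove the SAS from the scales that may be rated remotely, so that it is done at the next in-person visit. This reconciles the footnote with 8.2.7.2.3.
2. Whether or not the footnote can still be changed, state in SAP 10.5.3 that SAS total-score summaries use in-person assessments only, and that items rated remotely are listed separately.
3. In SAP 15.2, state that a remote SAS rating never replaces an in-person one in the same window.

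**Cost.** Some SAS totals will be missing at remote visits. Visit mode must be recorded or recovered from site records, since the documents mention no such indicator. The footnote change is a protocol amendment and needs the approvals in protocol 6.6. It cannot affect visits already held, and the SAP, dated 24 Jun 2024, refers to patients who had finished by 30 Apr 2024. The SAP changes are a few sentences and also work for data already collected, provided visit mode can be established.

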6.1 Overall Study Design and Plan

Study ITI-007-503 ("Study 503") is an international, open-label, multicenter, 6-month study to assess the safety and tolerability of lumateperone as adjunctive therapy in patients with MDD. The Study will be performed at approximately 120 study centers. No *de novo* patients will be enrolled.

Patients who have safely completed the lead-in studies may be eligible to participate in this Openlabel Safety Study. Lead-in study completion is defined as a patient who completes the doubleblind treatment period (ie, all scheduled visits up to and including Visit 8) of the lead-in study.

The study will be conducted as follows:

- A **Screening Period** of one day in duration. Potential patients rolling over from the leadin studies will be evaluated for eligibility during the Screening/Baseline Visit (Visit 1/Day 1) which is the same visit as Visit 8/Day 43 of the lead-in study. Patients who meet all eligibility criteria at the Screening/Baseline Visit (Visit 1/Day 1) will be dispensed lumateperone 42 mg to be self-administered each evening without respect to food.
- A **26-week Open-label Treatment Period** during which patients will self-administer lumateperone, to be taken each evening, without respect to food. Background ADT should also continue as previously prescribed, with no change of dose from the lead-in studies. Patients will attend visits on Weeks 1, 2, 3, 4, 6, 8, 10, 12, 14, 16, 18, 20, 22, 24, and 26. The Open-label Treatment Period will last a total of 26 weeks. A patient will be defined as a treatment completer if the patient completes the Open-label Treatment Period (all scheduled visits up to and including Visit 16/Week 26).
- A 2-week Safety Follow-up Period. A Safety Follow-up visit will occur approximately 2 weeks after completion of the Open-label Treatment Period or after the Early Termination (ET) Visit. Any ongoing AEs at the Safety Follow-up Visit must be followed until resolution, until the AE stabilizes, until it is determined to be not clinically significant, or until the patient is lost to follow-up.

Patients who prematurely discontinue should be seen for an ET visit as soon as possible and will also be asked to return to for a Safety Follow-up visit approximately 2 weeks after Visit 16/ET visit.

The maximum per-patient study duration for the Open-label Safety Study will be approximately 28 weeks.

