8.2.1.4 Time Period and Frequency of AE and SAE Reporting

The Investigator will report all AEs from the time informed consent was obtained until the final protocol-defined study visit or last known dose date of study drug + 1 day, whichever is later.

The Investigator will report all SAEs from the time informed consent was obtained until 30 days after the last known dose date of study drug.

At each visit, patients are to be queried regarding any AEs that have occurred since the previous visit. Patients will be asked to volunteer information with a nonleading question such as, "How do

you feel since your last visit?"

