8.2.7 Other Safety Assessments

8.2.7.1 Columbia-Suicide Severity Rating Scale

The C-SSRS is a clinician-rated instrument that reports the severity of both suicidal ideation and behavior (Posner et al, 2011). The C-SSRS will be completed by a trained and Sponsor-approved rater.

Suicidal ideation is classified on a 5-item scale:

- 1. Wish to be dead
- 2. Nonspecific active suicidal thoughts
- 3. Active suicidal ideation with any methods [not plan] without intent to act
- 4. Active suicidal ideation with some intent to act, without specific plan, and
- 5. Active suicidal ideation with specific plan and intent.

The C-SSRS also captures information about the intensity of ideation, specifically the frequency, duration, controllability, deterrents, and reasons for the most severe types of ideation.

Suicidal behavior categories are:

- Completed suicide
- Actual attempt
- Interrupted attempt
- Aborted attempt, and
- Preparatory acts or behavior

More than 1 classification can be selected provided it represents separate episodes. For actual attempts only, the actual or potential lethality is classified for the initial, most lethal, and most recent attempts.

The C-SSRS will be completed at all study visits. At Screening/Baseline (Visit 1/Day 1) and at all other visits, the C-SSRS will be completed for suicidal ideation and behavior since the previous visit ("Since Last Visit" version). Before the patient leaves the study site, the Investigator or appropriately qualified designee will assess the patient's C-SSRS results.

The patient should not be released from the study center until the results of the C-SSRS are reviewed and the patient is not considered to be at risk. If there is doubt about whether a patient is at risk, the Investigator must obtain appropriate psychiatric consultation. The results of the C-SSRS will be recorded in the eCRF. The C-SSRS will be completed by a trained and Sponsor-approved rater.

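### A remote visit held without a C-SSRS leaves the preceding 7 or 14 days outside every C-SSRS recall period, and the protocol does not settle whether such a visit is allowed

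*Protocol*

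**What the plan says.** Protocol Section 8.2.7.1 is unconditional: "The C-SSRS will be completed at all study visits". Table 1-1 marks the C-SSRS at all 17 visits, and each visit list in Section 8.4 includes it. The same section sets the recall period: at Visit 1 and all later visits, "the C-SSRS will be completed for suicidal ideation and behavior since the previous visit". It adds an on-site safeguard: "The patient should not be released from the study center until the results of the C-SSRS are reviewed".

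Table 1-1 footnote 2 covers the Open-label Treatment Period. If the patient cannot travel or the site cannot schedule an in-person visit, "sites will be permitted to conduct remote visits with approval from the Sponsor or designee". It makes local laboratory and ECG testing conditional on the investigator judging it clinically necessary, and then says: "Remote assessments of MADRS, CGI-S, C-SSRS, and AIMS, BARS, SAS may also be performed, if feasible". Visit 1 must be in person. The notes to SAP Table 2-1 repeat this text.

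SAP 10.5.4 tabulates emergence of suicidal ideation, serious ideation and behavior, and worsening of ideation, over the whole Open-label Treatment Period against a lead-in baseline. Neither that section nor the data-handling conventions in SAP Section 15 say what happens when a scheduled C-SSRS is missing.

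**The concern.** Footnote 2 and Section 8.2.7.1 do not refer to each other. A site that treats the footnote as governing remote visits could hold one without a C-SSRS and believe it had followed the protocol. Another site could read Section 8.2.7.1 and treat the same visit as a deviation.

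The recall anchor turns this into a measurement problem. The next C-SSRS looks back only to the remote visit, so nothing in the protocol tells the rater to recover the earlier interval. The review before release is written for a patient at the study center, and the text gives no counterpart for a remote patient.

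Safety is the primary objective, and Section 4 itself stresses suicide as a cause of death in severe depression. There is no data and safety monitoring board. Under Section 6.4.2 the quarterly safety review relies on the C-SSRS among other data. An event confined to an uncovered interval would be absent from the C-SSRS data in that review and from the SAP 10.5.4 counts.

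**Working it through.** The plan states no figure on this point, so the check is arithmetic on the schedule.

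**Inputs**
- Study days for Visits 1-17 (Table 1-1): 1, 8, 15, 22, 29, 43, 57, 71, 85, 99, 113, 127, 141, 155, 169, 183, 197.
- Spacing (Synopsis): "Patients will be seen for weekly visits through Visit 5/Week 4. Thereafter, visits will occur every two weeks".
- Visits that may be remote: Visits 2-16, that is, 15 visits. Visit 1 must be in person and Visit 17 lies after the treatment period.
- Visit window: ±3 days for every visit after Visit 1.
- Treatment period: 183 − 1 = 182 days.

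**Uncovered interval.** If visit k is held remotely without a C-SSRS, the next C-SSRS asks about the time since visit k. The interval not covered is day(k) − day(k−1).

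| Skip at | Visits | Gap | With windows | Share of 182 days |
|---|---|---|---|---|
| Visit 2 | 1 | 8 − 1 = 7 days | 4-10 | 7/182 = 3.8% |
| Visits 3-5 | 3 | 7 days | 1-13 | 3.8% |
| Visits 6-16 | 11 | 14 days | 8-20 | 14/182 = 7.7% |

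The windows add ±3 days at Visit 2, because Day 1 is fixed, and ±6 days elsewhere, because both ends can move. Two consecutive skips leave 14, 21 or 28 days, depending on where they fall.

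**Example.** Visit 7 is in person (Day 57). Visit 8 is remote without a C-SSRS (Day 71). Visit 9 (Day 85) asks about Days 71-85. No C-SSRS covers Days 57-71.

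**Other inquiry**
- Adverse events (Section 8.2.1.4): "At each visit, patients are to be queried regarding any AEs that have occurred since the previous visit". This covers the interval, but through a general, nonleading question.
- MADRS Item 10: suicidal thoughts only, not behavior. MADRS is scheduled at Visits 2-5, 7, 9, 11, 13, 15 and 16, and a remote MADRS falls under the same footnote clause.
- At Visits 6, 8, 10, 12 and 14 MADRS is not scheduled. At these 5 of the 11 two-week visits the C-SSRS is the only scheduled suicidality instrument.

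**Effect on SAP 10.5.4.** Each patient is classified by the most severe report in the period, against a baseline fixed in the lead-in study. Removing an interval can delete a qualifying report but cannot create one, so the error goes in one direction. It changes a patient's classification only if the sole or most severe occurrence lay in the gap; ideation that persisted past the remote visit would still be picked up.

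**With recall from the last completed C-SSRS.** The gap after one skip is 0 days. The next C-SSRS then looks back day(k+1) − day(k−1): 14 days after a skip at Visits 2-4, 21 days at Visit 5, and 28 days at Visits 6-16.

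**The case against.** The best defense is that footnote 2 permits a remote mode and waives nothing. No sentence says that the C-SSRS may be omitted, and the schedule and the visit lists all include it. This reading is tenable, so a reader should not infer that the protocol makes the C-SSRS optional. The other reading is tenable too: the preceding sentence accepts that laboratory and ECG assessments may be left out, feasibility is a condition, and the footnote uses mandatory language for Visit 1. The text does not settle the matter.

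Three further inferences go beyond the documents:
- That about two weeks are always lost. This is the figure for Visits 6-16; at Visits 2-5 it is about one week.
- That nobody asks about suicidality in the gap. This is true of the C-SSRS only, since the adverse event query and, where performed, MADRS Item 10 still ask in part.
- That the gap is invisible. C-SSRS results go into the eCRF, so a missing form can be seen visit by visit, and Section 9.7 requires deviations to be documented. What hides the gap is the period-level summary. Under the optional reading, the omission would not count as a deviation at all.

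The circumstances are also limited. Remote visits need a stated reason and approval from the sponsor or designee. If the whole visit is missed, the previous visit is the last one held and no gap arises. The gap also assumes that raters count a remote contact without a C-SSRS as the previous visit; the rater instructions are not among the documents. On risk review, Section 8.2.7.1 separately requires psychiatric consultation when risk is in doubt, and that sentence is not tied to the site.

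**Conclusion.** The point holds as an unresolved conflict between Section 8.2.7.1 and footnote 2, together with a recall rule that does not recover a missed assessment. One skipped remote C-SSRS leaves 7 days (Visits 2-5) or 14 days (Visits 6-16; 8-20 with windows) outside every C-SSRS recall period, which is 3.8% or 7.7% of that patient's 182-day treatment period. This rests on the literal recall wording and on a remote visit actually being held without the C-SSRS.

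The SAP 10.5.4 emergence and worsening counts can only be understated as a result. The documents give no frequency of remote visits or of skipped assessments, so the size cannot be estimated and nothing here shows that it is large. A reader might infer a material bias in the reported suicidality rates; the documents do not support that. They support a gap of known length per occurrence, unknown frequency and known direction, which a wording change would close.

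**What to change.** 1. In Section 8.2.7.1, run recall from the last completed C-SSRS instead of the previous visit. A missed assessment is then recovered at the next one under either reading of footnote 2. The downside is a longer recall period after a miss: 14, 21 or 28 days instead of 7 or 14. After a skip at Visit 16, recall at Visit 17 would span treatment and follow-up. SAP 10.5.4 reports these separately, so it should say to which period such a report belongs.
2. Reconcile footnote 2 and its copy under SAP Table 2-1 with Section 8.2.7.1 on whether the C-SSRS is required at remote visits. Keep the words that permit remote administration: that sentence is the only text allowing it, so simply deleting the C-SSRS from it would leave the conflict in place.
3. Reconcile the review-before-release text in Section 8.2.7.1 with remote visits. What that review should consist of is for the sponsor to decide.

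The cost is wording in the protocol and the SAP, and in the rater instructions where they repeat the recall rule. No visit or instrument is added.
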